16.1 AE Reporting

To the FDA: In accordance with FDA reporting requirements, all AEs occurring during the course of the clinical trial will be collected, documented, and reported by the PI or IND Sponsor. *On an annual basis*, as part of the update to the study IND, the IND Sponsor will submit to the FDA:

CONFIDENTIAL

This material is the property of the NYU School of Medicine and Langone Health
Do not disclose or use except as authorized in writing by the study sponsor

- A list of all AEs that have occurred during the reporting period
- A summary of all IND safety reports submitted during the past year
- A list of all subjects who died during the participation in the investigation, listing cause of death for each,
- And a list of subjects who dropped out during the course of the investigation in association with any adverse experience, whether or not thought to be drug related.

To the IRB: In accordance with local IRB requirements, all AEs occurring during the course of the clinical trial regardless of relationship to study activities will be collected, documented, and reported by the PI or designee to the IRB *on an annual basis* in the application for the study's continuation renewal. Staff education, re-training or appropriate corrective action plan will be implemented when unreported or unidentified AEs or SAEs are discovered, to ensure future identification and timely reporting.

To the DSMB: All AEs occurring during the course of the clinical trial regardless of relationship to study activities will be reported to the DSMB at regular meetings. Prior to each DSMB meeting, the PI will prepare a report to the Board including review of aggregate analysis of AEs and SAEs.

Following each meeting, the board will provide the PI with a report including a recommendation to continue the study unchanged, continue with modifications of the protocol and/or the consent form to protect participant safety, or terminate the study. This report will then be submitted to the FDA as part of the annual report to the study IND, and the IRB in the application for the study's annual continuation renewal.

To the Study Sponsors:

Tilray

The PI shall promptly inform Tilray of any significant safety issues occurring during the course of the study that might affect the performance of the study and of any AEs and SAEs experienced by subjects during the study. The PI shall share with Tilray any associated CRFs and source data, safety reports related to such AEs and SAEs, and permit access to anonymized pharmacokinetic data of study subjects.

PI shall provide all reports issued by the DSMB according to protocol (e.g. annually for the duration of the trial, including following completion of treatment for the first 5 completers, after completion of treatment for the first 20 completers, and upon completion of enrollment for the trial).

NIH/NIAAA

All AEs occurring during the course of the clinical trial regardless of relationship to study activities will be collected, documented, and reported by the PI or designee to NIH/NIAAA on an annual basis in the annual Research Performance Progress Report (RPPR).

16.2 SAE Reporting

SAEs will be promptly reported to the CRC and PI. The PI or qualified designee will distinguish Serious Adverse Events (SAEs) from Adverse Events (AEs). The details of the event will be documented and reported as follows:

To the FDA: The PI is required to report certain study events in an expedited fashion to the FDA. These written notifications of AEs are referred to as IND/IDE safety reports.

The following describes the IND safety reporting requirements by timeline for reporting and associated type of event:

- **Within 7 calendar days** (via telephone or facsimile report)
Any study event that is:
 - associated with the use of the study drug
 - unexpected, and
 - fatal or life-threatening
- **Within 15 calendar days** (via written report)
Any study event that:
 - associated with the use of the study drug,
 - unexpected, and

CONFIDENTIAL

This material is the property of the NYU School of Medicine and Langone Health
Do not disclose or use except as authorized in writing by the study sponsor

- serious, but not fatal or life-threatening
 - or-
- a previous AE that was not initially deemed reportable but is later found to fit the criteria for reporting (reporting within 15 calendar days from when event was deemed reportable).

Any finding from tests in laboratory animals that:

- suggest a significant risk for human subjects including reports of mutagenicity, teratogenicity, or carcinogenicity.

Each written notification must be submitted on an FDA Form 3500A. The PI is also required to identify in IND safety reports all previous reports concerning similar AEs and to analyze the significance of the current event in light of the previous reports.

To the IRB: The IRB Chair or Administrator will be notified immediately for SAEs that are at least possibly related to study participation only. If the IRB administrator determines that reporting of the incident/issue is required, it will be submitted to the IRB within 48 hours of the IRB direction/response.

The team will also submit summary information related to all SAEs, AEs, and UPs in the annual application for continuation to the IRB.

To the Study Sponsors:

NIH/NIAAA

SAEs considered at least possibly related to study participation will be documented and reported to NIAAA within 48 hours with copies included in the participant's file.

Tilray

If an SAE occurs after the subject signs informed consent through the end of study participation, the PI or a qualified designee will complete the Tilray SAE Form and send it via email to contacts designated by Tilray within 24 hours of the site becoming aware of the SAE. The form must be completed and submitted to Tilray any time a serious medical event has occurred in a participant during the clinical trial, whether or not it is considered related to the study treatment, including active comparators and placebo.

Ensure that an investigator has reviewed and signed the SAE form prior to submission.

Every exposure during pregnancy (participant) should be reported on an SAE worksheet as a case of special interest from the time of study enrolment to the end of study participation.

The following timelines describe when Tilray, as the manufacturer of IP, has to report ADRs to Health Canada:

- Fatal or life-threatening unexpected ADRs require notification of regulatory agencies as soon as possible but no later than 7 calendar days after first knowledge by Tilray that a case qualifies, followed by as complete a report as possible within 8 additional calendar days. The report will include an assessment of the importance and implication of the findings, including relevant previous experience with the same or similar medicinal products.
- All other serious, unexpected ADRs must be filed as soon as possible but no later than 15 calendar days after first knowledge by Tilray that the case meets minimum criteria for expedited reporting.

16.3 UP Reporting

Incidents or events that meet the OHRP criteria for UPs involving risks to subjects or others require notification of the local IRB. The phrase "unanticipated problems involving risks to subjects or others" is found but not defined in the HHS regulations at 45 CFR part 46. Any incident, experience, or outcome that meets all of the following criteria is considered to be Reportable New Information (RNI) and is required to be promptly reported to the local IRB:

- unexpected (in terms of nature, severity, or frequency) given (a) the research procedures that are described in the protocol-related documents, such as the IRB-approved research protocol and informed consent document; and (b) the characteristics of the subject population being studied;

CONFIDENTIAL

This material is the property of the NYU School of Medicine and Langone Health
Do not disclose or use except as authorized in writing by the study sponsor

- related or possibly related to participation in the research (in this guidance document, possibly related means that, in the opinion of the PI, the incident, experience, or outcome was more likely than not caused by procedures involved in the research); and
- suggests that the research places subjects or others at a greater risk of harm (including physical, psychological, economic, or social harm) than was previously known or recognized.

OHRP recognizes that it may be difficult to determine whether a particular incident, experience, or outcome is unexpected and whether it is related or possibly related to participation in the research. OHRP notes that an incident, experience, or outcome that meets the three criteria above generally will warrant consideration of substantive changes in the research protocol or informed consent process/document or other corrective actions in order to protect the safety, welfare, or rights of subjects or others.

The RNI report will include the following information:

- Protocol identifying information: protocol title and number, PI's name, and the IRB project number;
- A detailed description of the event, incident, experience, or outcome;
- An explanation of the basis for determining that the event, incident, experience, or outcome represents an UP;
- A description of any changes to the protocol or other corrective actions that have been taken or are proposed in response to the UP.

UPs must be reported using the following timeline:

- UPs that are SAEs will be reported to the IRB and to the study sponsor according to SAE reporting procedures described above (within 48 hours of the investigator becoming aware of the event).
- UPs that meet the requirements for RNI will be reported to the IRB as soon as possible and within 5 working days of the site becoming aware of the event.
- All other UPs not related to study activities or that do not result in harm to participants will be reported to the IRB annually in the application for the study's continuation renewal.

16.4 Pregnancy Reporting

Pregnancy information on clinical study subjects is collected by the investigator. If a subject should become pregnant during the course of the study, the investigator or qualified designee will contact the IRB within 5 working days of the PI or qualified designee first becoming aware of the pregnancy.

Tilray Pregnancy Reporting Requirements: Every exposure during pregnancy (participant) should be reported on a Tilray SAE worksheet within 24 hours of the site becoming aware of the pregnancy as a case of special interest from the time of study enrollment to the end of study participation. If an SAE occurs in conjunction with the pregnancy, then the Tilray reporting timeframe for an SAE (24 hours) must be met. In the event of a pregnancy, administration of study medication will be discontinued, but all other follow-up data, including safety data, will be collected.

Pregnancies resulting in congenital abnormalities or birth defects in offspring meet the requirements for an SAE and will be collected, documented, and reported according to the procedures outlined above for SAEs.

17 Reporting of Investigational Medicinal Product Quality Complaints

17.1 Defect or Possible Defect in the IP

Any defect or possible defect in the investigational medicinal product (defined as a pharmaceutical form of an active substance or placebo being tested or used as a reference in a clinical trial) must be reported by the PI or qualified designee to Tilray within 48 hours of first becoming aware of the possible defect. This report to Tilray may be made by telephone or by email. The product and packaging components in question, if available, must be stored in a secure area under specific storage conditions until it is determined whether the product is required to be returned for investigation of the defect. If the product complaint is associated with an SAE, the SAE must be reported separately in accordance with the protocol, and the SAE report should mention the product quality complaint.

CONFIDENTIAL

This material is the property of the NYU School of Medicine and Langone Health
Do not disclose or use except as authorized in writing by the study sponsor

17.2 Temperature Deviations

In the event that the temperature at which the IP is stored is less than 2°C or greater than 8°C, the CRC and PI will be notified immediately and a temperature deviation form will be completed and sent via email to contacts designated by Tilray as soon as possible. Tilray will provide further guidance on how to proceed on a case-by-case basis.

18 Study Halting Rules

When three severe AEs are determined to be “probably related” to the study agent, the DSMB will be informed and asked to convene in order to determine whether action should be taken. The Principal Investigator will inform the DSMB members within 24 hours of this occurrence and will provide the DSMB with AE listing reports. The DSMB will convene an ad hoc meeting by teleconference or in writing as soon as possible. The DSMB will provide recommendations for proceeding with the study to the Principal Investigator. The Principal Investigator will inform the FDA of the DSMB’s decision and the disposition of the study. If the DSMB finds it is likely that CBD is contributing to negative outcomes, they will consider solutions including protocol changes or potentially stopping the study.

19 Safety Oversight

Medical and Safety Monitoring

The research team (project manager, coordinators, and research assistants) will submit any adverse events to the PI. The PI is responsible for reviewing all AEs and serious adverse events (SAEs) reported. All SAEs will be reviewed at the time they are reported in the electronic data capture system. All AEs will be reviewed on a weekly basis to observe trends or unusual events.

The PI will generate and present reports for Data Safety Monitoring Board (DSMB) meetings. The DSMB will receive listings of AEs and summary reports of all SAEs at a frequency requested by the DSMB, but at least annually. Furthermore, the DSMB will be informed of expedited reports of SAEs.

Data and Safety Monitoring Board (DSMB)

A Data and Safety Monitoring Board (DSMB) will be established, comprising three individuals appointed by the PI. The members of the DSMB will have the following backgrounds/expertise: one member with expertise in clinical trials for alcohol use disorder, one member with expertise in clinical trials involving pharmacological interventions, one member with expertise in clinical trials for mood disorders, and one member with expertise in clinical trials for anxiety disorders. This committee will meet (in person or by teleconference) prior to enrollment of the first participant, and at least annually thereafter, including meetings following completion of treatment of the first 5 completers, after completion of treatment of the first 20 completers, and upon completion of enrollment for the trial. Prior to each meeting, the PI will prepare a report to the Board including review of:

- Protocol and ICF changes
- Protocol violations and deviations
- Documentation of informed consent
- Enrollment and retention
- Investigator or key personnel changes
- Aggregate analysis of adverse events/serious adverse events
- Protection of confidentiality

Following each meeting, the board will provide the PI with a report including a recommendation to continue the study unchanged, continue with modifications of the protocol and/or the consent form to protect participant safety, or terminate the study.

20 Clinical Monitoring

Site staff will be required to audit source documentation, including informed consent forms and HIPAA forms, regulatory documents and case report forms on a biannual basis. Site staff will be responsible for local quality

CONFIDENTIAL

This material is the property of the NYU School of Medicine and Langone Health
Do not disclose or use except as authorized in writing by the study sponsor

assurance and will verify that study procedures are properly followed and that site staff are trained and able to conduct the protocol appropriately. If the site staff's review of study documentation indicates that additional training of study personnel is needed, this will be arranged as per the PI. Study team members will review each other's data for completeness, accuracy, and fidelity to the protocol.

21 Statistical Considerations

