7.2 Study Agent Accountability Procedures

CBD will be stored by the study personnel securely under the PI's individual schedule 1 DEA registration and New York Bureau of Narcotics Enforcement (BNE) class 7 license in accordance with all applicable laws and regulations. Additionally, a NYS BNE class 9 importer license and a DEA importer permit will be obtained by

CONFIDENTIAL

This material is the property of the NYU School of Medicine and Langone Health
Do not disclose or use except as authorized in writing by the study sponsor

the schedule I license and registration holder prior to importation of study drug and study initiation. CBD will be stored in a double-locked refrigerator. The refrigerator is located in a designated research room, with limited access to the PI and study staff only, within the NYU-HHC CTSI Facility, which is located at [name]. The Primary Investigator will oversee the appropriate storage, accountability and dispensing of the study medication and all study drug administration to the patients will be done by the PI or treating co-investigators. In order to preserve the blind, medication will be administered in identical capsules containing 0 or 200 mg of CBD dissolved in a mixture of self-emulsifying excipients; participants will be delivered multiple 200mg capsules/day for a total of 0, 600, or 1200 mg CBD/day.

Study medication will be received under a Schedule 1 import license obtained by the PI and will be logged into the approved storage facility upon arrival. Study medication will be re-packaged by unblinded study personnel from the original Tilray bottles into blinded and appropriately labeled bottles for dispensation. The re-bottled, blinded study medication will then be dispensed to participants under the direct supervision of the PI or a designated coinvestigator, as approved by the BNE and DEA. Participants will be required to return all un-used medication, which will be kept securely at the drug storage site until it is sent to a reverse distributor for destruction.

Designated study personnel will keep a log of the study drug accountability and dispensing in accordance with New York State Bureau of Narcotic Enforcement and DEA policies (see below). This process will provide strict safeguarding and accounting of the agent both for internal and external regulatory agencies.

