12.3 Relatedness

This category provides the opportunity to indicate the reasons for suspecting a drug-related effect. If no such effect is suspected, check “No.” The following reasons for possible relationship to drug are to be assessed by the medically qualified investigator.

CONFIDENTIAL

This material is the property of the NYU School of Medicine and Langone Health
Do not disclose or use except as authorized in writing by the study sponsor

Dose-response: indicates that the intensity of the event is related to the dosage level.

Timing of onset: is used if the onset of the event has some regular relationships to drug administration (e.g., it always occurs 1 hour after taking the drug).

Known drug effect: is another reason for suspecting a drug relationship.

The relationship of each AE to study drug will be assessed using the following terms and definitions:

Probable (must have first two): This category applies to AEs that are considered, with a high degree of certainty, to be related to the study drug. An AE may be considered probable, if:

- It follows a reasonable temporal sequence from administration of the drug.
- It cannot be reasonably explained by the known characteristics of the subject's clinical state, environmental or toxic factors, or other modes of therapy administered to the subject.
- It follows a known pattern of response to the suspected drug.

Possible: This category applies to those AEs in which the connection with the study drug administration is possible. An AE may be considered possible if, or when, any of the above reasons have been selected.

Unrelated: This category is applicable to those AEs that are judged to be due only to extraneous causes (e.g., disease, environment, etc.) and do not meet any of the criteria for a possible drug relationship.

The determination of the relationship of the AE to the use of the study drug(s) rests on careful medical consideration of the PI.

13 Monitoring Adverse Events

The investigator will follow all AEs until the event is resolved, stabilized, or the subject is lost to follow-up. Relevant clinical assessments and laboratory tests may be performed as determined by the PI or a qualified designee, appropriate medical intervention should be provided and, if necessary, the subject may be excluded from additional treatment with the study drug.

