21.3.7 Planned Interim Analysis

21.3.7.1 Safety Review

The DSMB will meet (in person or by teleconference) following completion of treatment of the first 5 completers, after completion of treatment of the first 20 completers, and upon completion of enrollment for the trial. Prior to

CONFIDENTIAL

This material is the property of the NYU School of Medicine and Langone Health
Do not disclose or use except as authorized in writing by the study sponsor

each meeting, the PI will prepare a report to the Board including review of the aggregate analysis of adverse events/serious adverse events.

Following each meeting, the board will provide the PI with a report including a recommendation to continue the study unchanged, continue with modifications of the protocol and/or the consent form to protect participant safety, or terminate the study. The study may be stopped if there are untoward and concerning levels of AE or SAE outcomes attributable to CBD or study participation. If the DSMB finds it is likely that CBD is contributing to negative outcomes, they will consider solutions including protocol changes or potentially stopping the study.

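### Two milestone DSMB reviews are timed by completers, so they slip as drop-out rises, and no arm-level safety data are specified for the board

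*Combined protocol and SAP*

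**What the plan says.** Section 19 (Safety Oversight) has the board meet "prior to enrollment of the first participant, and at least annually thereafter", with milestone meetings "including meetings following completion of treatment of the first 5 completers, after completion of treatment of the first 20 completers", and again when enrolment is complete. Section 21.3.7.1 repeats the two completer milestones and the end-of-enrolment meeting.

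The PI writes and presents the report: "The PI will generate and present reports for Data Safety Monitoring Board (DSMB) meetings", and "Prior to each meeting, the PI will prepare a report to the Board including review of" a list of items. The safety item on that list is "Aggregate analysis of adverse events/serious adverse events"; enrolment and retention is another item. Section 16.1 describes the same content. No section mentions tables by arm, a closed session or an independent statistician.

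The board's task is causal. Section 21.3.7.1 says what it will consider "If the DSMB finds it is likely that CBD is contributing to negative outcomes". Under Section 12.3, "The determination of the relationship of the AE to the use of the study drug(s) rests on careful medical consideration of the PI". The trial is double-blind (Section 5.1), and Section 7.2 keeps the code with separate staff: "Study medication will be re-packaged by unblinded study personnel" before the blinded bottles are dispensed under supervision of the PI or a co-investigator.

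Other safety routes exist. Section 18 convenes the board after three severe AEs judged probably related, with notice within 24 hours. Section 19 gives it AE listings and SAE summaries as often as it asks and at least yearly, and word of expedited SAE reports. Section 16.1 sends all AEs to its regular meetings.

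**The concern.** Two features of the rule work against its purpose.

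First, a review timed by completers is delayed by the thing it should detect. If side effects make people stop before T7, more participants must be randomised before the 5th or 20th completer accrues. Section 6.6.2 says that those who leave will not be replaced, so the second milestone may never be reached.

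Second, whether CBD is contributing to harm is, in a placebo-controlled trial, a between-arm question. The protocol treats it so at the end: Section 21.3.2 compares the number of adverse events between groups for Hypothesis 1c. During the trial the board is asked a similar question with no arm-level data specified. The PI cannot supply them without losing the blind under which relatedness is judged.

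At stake is how many participants are exposed before a scheduled look, and whether that look can separate drug effect from background. Section 21.3.8 describes the primary outcomes as safety data, so this is central to the trial.

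**Working it through.** The protocol gives no operating characteristics for the DSMB reviews, so there is no stated figure to reproduce.

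**Inputs from the protocol.** 40 randomised 1:1 (Section 5.1); recruitment September 2019 to August 2021, about 24 months (Section 6.3); treatment 8 weeks (Section 7.1.9); milestones at 5 and 20 completers (Sections 19 and 21.3.7.1).

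**Assumptions.** Even accrual, and a drop-out proportion *d* from 0 to 50%.

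**Timing.** Accrual is 40/24 = 1.67 per month. Eight weeks is 56/30.44 = 1.84 months, during which 1.67 × 1.84 = 3.07 more are randomised. The number randomised when the *k*-th completer finishes is about *k*/(1 − *d*) + 3.07, capped at 40. The chance of ever having 20 completers is P(X ≥ 20), with X binomial (40, 1 − *d*).

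| Drop-out *d* | Randomised at 5-completer review | Randomised at 20-completer review | Month of 20-completer review | P(20 completers ever reached) |
|---|---|---|---|---|
| 0% | 8.1 | 23.1 | 13.8 | 1 |
| 20% | 9.3 | 28.1 | 16.8 | >0.999 |
| 30% | 10.2 | 31.6 | 19.0 | 0.998 |
| 40% | 11.4 | 36.4 | 21.8 | 0.926 |
| 50% | 13.1 | 40 (cap) | 25.8 | 0.563 |

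Example at 30%: 20/0.7 = 28.6, and 28.6 + 3.07 = 31.6. Non-attainment is 1 − 0.926 = 7% at 40% and 1 − 0.563 = 44% at 50%.

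**Unequal drop-out.** Take 40% on CBD and 10% on placebo, so 25% overall. The 20th completer is about the 20/0.75 = 26.7th randomised, and the review falls at about 29.7. CBD makes up 0.6/(0.6 + 0.9) = 40% of completers. About 26.7/2 × 0.4 = 5.3 CBD participants have dropped out before the trigger is met. Simulation (10,000 runs) gives the same values.

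**What a pooled rate shows.** With 1:1 allocation, AE risks of 10% on placebo and 40% on CBD pool to (10 + 40)/2 = 25%, the same as 25% in both arms.

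**The ad hoc trigger as a backstop.** Suppose each of 20 CBD participants has at most one severe, probably related AE, with probability 5%, 10% or 20%. The chance of at least three is 0.075, 0.323 or 0.794. AEs below severe that lead people to stop do not count toward it.

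**Re-timed milestones.** If the count includes everyone who has completed or permanently stopped, the reviews fall no later than about 5 + 3.07 = 8 and 20 + 3.07 = 23 randomised, whatever the drop-out.

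**The case against.** The strongest reply is that the completer milestones are only part of the oversight. The board also meets before enrolment, at least yearly and at the end of enrolment. It is convened ad hoc under Section 18, sets the frequency of its AE listings and hears of expedited SAEs. All AEs are reported to it, its report covers retention, and Section 6.6.2 continues safety follow-up after withdrawal. This stands. A reader might infer that reviews are triggered by completers alone, or that harm in drop-outs can be missed. The documents support neither: such events are in the board's data, and the yearly and end-of-enrolment meetings limit the delay.

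A reader might also take the aggregate analysis to mean pooled data only, and conclude that the board cannot do its job. The protocol does not define the word that way and does not bar the board from asking for arm-level data. What can be said is that by-arm reporting is not specified on any route. That the PI is blinded is likewise an inference from the double-blind design and the separate re-packaging staff.

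The size also depends on drop-out. No rate is stated, and failure to reach 20 completers matters only around 40% or more; at 30% it has probability 0.002. Nor would a by-arm table at the second milestone be decisive: with 10 per arm, Fisher's exact test at two-sided 0.05 has power of about 0.15 for 40% against 10%. That limits formal testing, but the board would still see the direction and type of any imbalance.

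**Conclusion.** The point holds as a cheap improvement. Two of the scheduled reviews are later the worse the drop-out: under even accrual, the second moves from about 23 of 40 randomised to about 28, 32 or 36 at 20%, 30% or 40%. It is never reached in about 7% of trials at 40% and 44% at 50%. The accrual pattern and every drop-out rate are assumptions. Separately, the board is asked to judge CBD's contribution to harm and no route specifies arm-level data. The other meetings and reports reduce the consequence to later and less informative milestone reviews; they do not supply the arm-level view.

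**What to change.** 1. In Sections 19 and 21.3.7.1 (and the matching text in Section 16.1), trigger the two milestone reviews when the 5th and the 20th participant has completed or permanently stopped study treatment. Define completion once: Sections 6.6.2 and 7.1.9 run the treatment phase through T7, Section 21.3.5 through T8.
2. Add a closed table of AEs, SAEs and discontinuations by masked arm (A/B), for the DSMB only. It would use the allocation code held by the existing unblinded re-packaging personnel (Section 7.2), who should take no part in AE assessment or data review. The PI supplies only the pooled open report.

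Neither change needs extra participants or visits. The cost is a few hours of existing unblinded staff time per review, and milestone reviews with somewhat fewer completers: about 20 × (1 − *d*) = 16, 14 or 12 at the second review for 20%, 30% or 40% drop-out. There is also a small risk that allocation leaks. It needs explicit control, because Section 20 has team members checking each other's data.
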